**Principal Investigator: [name]**

**Sub-Investigator: [name]**

**Sponsor or funding source: Stryker Endoscopy, San Jose, CA**

### **Background, Rationale and Context**

Knee arthroscopy procedures provide a minimally invasive method to assess the status of the knee joint in order to repair injuries of the meniscus and articular cartilage. In the past, two or more small openings in the skin (portals) were required in order to allow the passage of both an arthroscope to provide visualization of the knee joint and the instrument used to complete the surgical repair process. However, recent innovations in arthroscopy instrumentation have resulted in the ability to use one portal for knee arthroscopy procedures with both the arthroscope and the instruments passed into the knee joint through the same portal. Both uniportal and two portal arthroscopic techniques are used currently for knee arthroscopy procedures in the Department of Orthopaedic Surgery at Wake Forest Baptist Health.

### **Objectives**

This randomized, controlled clinical trial will compare the outcomes of single portal versus two portal techniques in patients who have meniscus or articular cartilage pathology. The study hypothesis is that patients who undergo single portal arthroscopy will have less pain post-operatively, use less pain medication, and have a higher International Knee Documentation Committee (IKDC) score at six months and one year compared to patients who undergo traditional two portal knee arthroscopy.

### **Methods and Measures**

**Design:** A randomized, controlled trial

**Setting:** Academic Medical Center: single study site at Wake Forest Baptist Health

### **Subjects selection criteria**

#### **Inclusion Criteria**

- Men and women between 21 and 65 years of age, who agree to comply with the protocol
- Patients undergoing a primary knee arthroscopy procedure for meniscus or articular cartilage pathology

#### **Exclusion Criteria**

- Patients with a history of long term pain medication use and/or chronic pain conditions unrelated to the surgery.
- Subjects with severe renal disease, allergies to pain medication, and subjects that will have adverse drug-drug reactions from prescribed pain medication.
- Patients with previous reconstructive procedures, lateral retinacular release, or microfracture
- Active knee infection or sepsis at the time of surgery
- Meniscal injuries requiring repair
- Ligamentous instability
- Advanced degenerative or inflammatory arthritis
- Known cancer at the time of surgery
- Conditions that might interfere with recovery from knee arthroscopy (i.e. conditions or diseases of the nervous and/or muscular system, vascular disease, uncontrolled diabetes)
- Malignant tumor history or treatment of malignant tumor of the knee
- Lower extremity condition causing abnormal ambulation (e.g. ankle fusion, ankle arthroplasty, previous hip fracture, knee arthrofibrosis)
- Pregnant, breast feeding, or planning on becoming pregnant during the time frame of the study, (if a woman of child-bearing age)
- Emotional or neurological conditions that affect the subject's ability or willingness to participate in the study including mental illness or drug and/or alcohol abuse
- Severely overweight (BMI >40) at study enrollment or surgery
- Currently participating in another research study
- Prisoner or impending imprisonment
- Workers' Compensation claims

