### **Sample Size:**

Power calculations were performed based on data from previous studies. Van de Graaf found a standard error of the mean (SEM) of 5.3 and a smallest detectable difference (SDD) of 14.6 for the Subjective Knee Evaluation Form part of the International Knee Documentation Committee (IKDC).(2) These measures were slightly larger than the SEM of 4.6 and the SDD of 9.0 reported by Irrgang.(1) Based on these values, power calculations identified the desired sample size as 50 patients in each surgical group to yield 84.7% power to detect a difference with an alpha = 0.05. In order to account for 10% missing data due to patient drop-outs and/or loss to follow-up, a total of 110 patients will be randomized and enrolled with 55 patients in each of the two surgical groups. The blocked randomization scheme will be designed for the potential enrollment of 60 patients in each of the two study groups.

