## Interventions and Interactions

### Evaluation Schedule Summary:

Evaluation	History / Pre-Op	Intra-Op	1 day	4 days	1 week	30 days ± 7 days	3 months ± 2 weeks	6 months ± 2 weeks	1 year ± 1 month
Patient • IKDC demographics	X								
• IKDC current health	X							X	X
• IKDC subjective knee evaluation	X					X	X	X	X
Patient phone calls • Pain scores/pain medication log			X	X					
Physician • IKDC knee history	X								
• IKDC surgical documentation form		X							
• IKDC knee examination form	X					X	X	X	X
• Document rehab duration						X	X		
Stitch Removal/ Postop Follow-up for Pain/Meds					X				

The study will include six visits: one pre-surgery visit and five post-surgery visits at one week, 30 days, three months, six months, and one year. The one week, 30 day, and three month follow-up visits coincide with the standard of care follow-up visits for patients who undergo knee arthroscopy. The six month and one year visits will be for research purposes and will not be billed to insurance providers.

Additionally, the patients will be contacted by phone at 1 and 4 days after surgery to determine their visual analog pain scores and their use of pain medications. Patients will also keep a daily log of their pain level and use of pain medications. These calls will also be used to remind patients to complete their pain diaries.

*Randomization:* A blocked randomization scheme (block size of 10) will be used to assign study participants to either single portal (Group 1) or two portals (Group 2) knee arthroscopy. Prior to surgery, the surgeon will log on to the randomization website to determine each participant's surgical group assignment. After randomization for each patient is complete, the website will document the name of the person who logged on to perform the randomization, the date and time of the log in, and the surgical group assignment for each patient. In addition, the website will document the patient's name, medical record number, and study treatment allocation. This randomization information will be forwarded to the operating room staff so that they can prepare for each study participant's surgical procedure.

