### **Subject Recruitment Methods**

The study will recruit patients who present to the Orthopaedic Sports Medicine Clinic at Wake Forest Baptist Health with symptoms requiring arthroscopic knee surgery for meniscal or articular cartilage pathology.

**Study screening and enrollment:** Potential study participants will be screened in the Orthopaedic Sports Medicine Clinic. Patients with meniscus injuries who meet the study inclusion criteria will be told about the study and will be asked if they would like to participate. The study will be described, and the requirements for study participation will be explained. Potential study participants will be encouraged to ask questions about the study and to find out what is involved in study participation. A patient information sheet will be provided to the potential subject to explain the study and used as a recruitment tool. Patients who agree to

participate will be asked to provide informed consent. No study related procedures will occur until after the informed consent is obtained. Following completion of informed consent, the study participants will be asked to complete three of the six IKDC forms including questionnaires to document demographics, current health, and subjective knee evaluations.

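### Eligibility can lapse after allocation, in the hands of a surgeon who knows the arm, and no rule keeps such patients in the trial

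*Combined protocol and SAP*

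**What the plan says.** **Exclusion Criteria.** Two exclusions are tied to surgery: "Active knee infection or sepsis at the time of surgery" and "Known cancer at the time of surgery". A third applies at either of two times: "Severely overweight (BMI >40) at study enrollment or surgery". A fourth, "Meniscal injuries requiring repair", carries no time and no method of assessment.

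**Subject Recruitment Methods.** Eligibility is first looked at well before the operation: "Potential study participants will be screened in the Orthopaedic Sports Medicine Clinic".

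**Interventions and Interactions, Randomization paragraph.** "Prior to surgery, the surgeon will log on to the randomization website to determine each participant's surgical group assignment". No day or window is given, and no confirmation of eligibility is required at log-in. The result travels ahead of the patient: "This randomization information will be forwarded to the operating room staff so that they can prepare for each study participant's surgical procedure". The website does record the date and time of each log-in.

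**Cross-over paragraph, directly after Randomization.** A change of technique during surgery, in either direction, is recorded as a cross-over on condition that the patient still satisfies the entry criteria. Cross-overs stay in the study. Nothing is said about a patient who fails that condition.

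**Human Subjects Protection.** Patients may withdraw at their own request and are otherwise followed according to the protocol. Withdrawals are not replaced.

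**Analytical Plan.** No analysis population is named.

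**The concern.** Randomization protects the comparison only if what happens to a patient after allocation does not decide whether that patient is counted. Here at least three criteria are worded so that they can be met on the day of surgery, and allocation may already have been drawn by then. Under the repair criterion, a tear may be judged to need repair once the joint is in view. That the question may be settled at arthroscopy is an inference; the protocol does not say so.

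The person making these judgements drew the allocation and is carrying out the assigned technique. If a finding of ineligibility leads to removal, one technique could lead to more such findings than the other, or to findings in different kinds of patient. The groups compared would then no longer be those that were randomized, and a larger sample would not correct this.

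There is also a smaller cost in numbers, because the recruitment allowance was made for something else: "In order to account for 10% missing data due to patient drop-outs and/or loss to follow-up".

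**Working it through.** **1. Order of events.**

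| Step | When | Eligibility check required? |
|---|---|---|
| Screening | Clinic | Yes |
| Log-in and allocation by the surgeon | Before surgery, time not fixed | None stated |
| Allocation sent to operating room | After log-in | None stated |
| Infection and known cancer | At the time of surgery | Criteria apply here |
| BMI above 40 | Enrollment or surgery | Criterion applies at both |
| Meniscal repair needed | Not stated | Not stated |
| Change of technique | During surgery | Patient must still qualify to be recorded as a cross-over |

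The last row matters most. It shows that the protocol expects eligibility to be reconsidered after allocation, and it deals only with patients who pass.

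**2. Bias.** Suppose a share f1 of one arm and f2 of the other is removed, and in both arms the removed patients' mean IKDC score lies D points below that of those retained. Each retained mean then exceeds its full-arm mean by f × D, so the treatment difference shifts by (f1 − f2) × D. The documents give neither f nor D. For scale only, take f1 − f2 = 10 percentage points and let D equal either smallest detectable difference cited under Sample Size. The shift is 0.10 × 9.0 = 0.9 points or 0.10 × 14.6 = 1.46 points. If removal is equal and D is the same in both arms, the shift is zero.

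**3. The plan's own figures.** Sample Size gives 50 evaluable per group, 84.7% power, alpha 0.05 and 110 randomized. Allowing for 10% loss, 50 / 0.9 = 55.6, so 56 per group or 112 in all. The stated 110 is within two patients of this. The 84.7% cannot be rebuilt from the stated inputs, because no between-patient standard deviation and no target difference are given. Solving backwards (two-sample t-test, two-sided alpha 0.05, 50 per group) gives a standardized difference of about 0.603.

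**4. Power if patients are removed.** Let x be the share of randomized patients removed as ineligible at surgery (assumed; no rate is given). Evaluable n per group = N × 0.9 × (1 − x), with the standardized difference held at 0.603.

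| x | n per group, N = 55 | Power | n per group, N = 60 | Power |
|---|---|---|---|---|
| 0% | 49.5 | 84.3% | 54.0 | 87.4% |
| 5% | 47.0 | 82.4% | 51.3 | 85.6% |
| 10% | 44.6 | 80.3% | 48.6 | 83.7% |
| 15% | 42.1 | 78.0% | 45.9 | 81.5% |

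The N = 60 columns apply only if the spare places in the randomization scheme were used. Sample Size builds the scheme for up to 60 per group but does not say what the extra places are for.

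**5. Number to randomize to keep 50 evaluable per group.** 50 / (0.9 × (1 − x)), rounded up and doubled: 118 at 5%, 124 at 10%, 132 at 15%. The 120 places would cover the first but not the other two.

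**The case against.** **The criteria do not have to wait for surgery.** A reader might infer that all four exclusions can be judged only at or during the operation. The documents do not support that. BMI is also applied at enrollment, known cancer is a matter of history, and BMI and infection can both be checked before log-in. The repair criterion mentions no time at all. This objection stands. For the three timed criteria the gap is narrower: no check is required before log-in, and the log-in time is not fixed. A same-day log-in would satisfy the present wording, and so would one made well ahead.

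**Removal is not stated.** A reader might infer that the protocol orders ineligible patients to be dropped. It does not. Human Subjects Protection can be read as keeping in follow-up everyone who has not withdrawn, and the no-replacement rule concerns withdrawals only. The cross-over condition, taken literally, also refers to the inclusion list rather than the exclusions. However, the recruitment section uses the same term for entry criteria generally, and making retention of cross-overs depend on continued eligibility invites the opposite reading. With no analysis population named, nothing settles the matter. This objection limits the point to what the plan permits.

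**The power loss is small and assumed.** This also stands. The rates are illustrative, the effect size is back-solved from a figure that cannot be reproduced, and the spare places would offset much of the loss. The figures do not show an underpowered trial.

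**The trial is closing.** The Update to the study protocol says that the sponsor has withdrawn support. This limits what can still be changed but does not affect how the randomized patients should be analysed.

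**Conclusion.** The concern holds in a limited form. The plan allows eligibility to be reassessed after allocation by a surgeon who knows the arm, fixes neither the time of allocation nor a check before it, and gives no rule for a randomized patient found ineligible. The weakness goes beyond missing detail, because following the text as written can lead to removal that differs by arm.

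The main risk is bias of unknown size and direction, and it arises only if patients are actually removed and removal is related to arm. The documents do not show that this happened. The effect on power is secondary: about 2 to 6 percentage points below 84.3% at assumed removal rates of 5% to 15%, and less if the spare places were used. The plan should be corrected on this point, but the problem does not by itself invalidate the design.

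**What to change.** 1. **Randomization paragraph.** Set the log-in to the day of surgery, after the BMI, infection and cancer criteria have been confirmed on a checklist. The website's time stamp allows this to be audited.
2. **Exclusion Criteria and cross-over paragraph.** State that the repair exclusion is judged on pre-operative assessment. Delete the condition that a cross-over must still qualify. State that every randomized patient stays in follow-up and in the primary analysis in the assigned group, whatever is found at surgery. Record repairs found during surgery on the existing IKDC Surgical Documentation Form and report them by arm.

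The retention rule is the essential part; a checklist alone does nothing about a finding made during the operation. None of this constrains what the surgeon does for the patient.

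**Cost.** A wording amendment and a short checklist. A few patients with an unplanned repair will stay in and may add variability. Operating room staff will learn the arm on the day, so both set-ups must be available.

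**Patients already allocated.** Given the close-out, only the retention, analysis and reporting rule applies: analyse all randomized patients as assigned, and report by arm any found ineligible after allocation. Parts 1 and 2 in full matter for any continuation or reuse of the protocol.

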### **Sample Size:**

Power calculations were performed based on data from previous studies. Van de Graaf found a standard error of the mean (SEM) of 5.3 and a smallest detectable difference (SDD) of 14.6 for the Subjective Knee Evaluation Form part of the International Knee Documentation Committee (IKDC).(2) These measures were slightly larger than the SEM of 4.6 and the SDD of 9.0 reported by Irrgang.(1) Based on these values, power calculations identified the desired sample size as 50 patients in each surgical group to yield 84.7% power to detect a difference with an alpha = 0.05. In order to account for 10% missing data due to patient drop-outs and/or loss to follow-up, a total of 110 patients will be randomized and enrolled with 55 patients in each of the two surgical groups. The blocked randomization scheme will be designed for the potential enrollment of 60 patients in each of the two study groups.

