## **Outcome Measures**

### **Patient assessments:**

Patients will complete the patient-related IKDC questionnaires at each study visit except the one week visit. The IKDC is used to monitor knee symptoms, function, and activity level (1) The IKDC was developed and revised by knee experts as a knee-specific rather than a disease-specific evaluation. (1) A recent study by Van de Graff, et al demonstrated that the IKDC was better in all its measurement properties than the KOOS or the WOMAC for evaluating patients with meniscal injuries. (2)

At the pre-surgery visit, study participants will complete several components of the IKDC questionnaires including the demographic form, current health assessment form, and the subjective knee evaluation form. Patients will maintain a daily log to document their use of pain medications for the first two weeks after surgery. In addition, study participants will complete the subjective knee evaluation form at one month, three months, six months, and one year.

Patients will be contacted by phone on post-surgical days 1 and 4 to remind them to complete their daily log and to report their pain level and medication use. At each phone call and clinic visit, patients will be asked two questions: *1. What day did you feel that you had completed recovering from the surgery?* and *2. What day did you stop taking pain medicine?* Patients also will be asked these questions at the 30 day clinic visit.

If patients are unable or decline to return to clinic for follow-up, we will try to collect the patient-completed questionnaires either by telephone, by mail, or by a web-based link sent to them via a REDCap database survey at any study time point.

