### **Analytical Plan**

**Primary outcome:** The IKDC Subjective Knee Evaluation Form score will be the primary outcome measure. The IKDC subjective knee form contains 19 questions and requires approximately five minutes to complete.(2) All except one of the items is converted to a score; a

maximum score of 100 indicates that the patient has no restrictions in their daily activities or sports and does not have any knee symptoms.(2)

**Secondary outcome:** Pain levels and the use of pain medication will be monitored by study participants using a daily pain diary. The pain diary will be used for the first two weeks after surgery. Pain levels will also be collected at the 1 and 4 day telephone calls. A pain rating will also be collected at the one week, 30 day, three months, six months, and one year visit.

**Data management:** All study data will be entered into a REDCap database. The database will be HIPAA compliant and will meet all the requirements of the NIH and FDA. The REDCap server is behind a firewall and is backed up every 24 hours. The data will be sent as an Excel spreadsheet for analysis to biostatisticians in the Section on Biostatistics of the Department of Public Health Sciences at Wake Forest School of Medicine.

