### **Update to the study protocol:**

The study sponsor, Stryker, Inc. has made a business decision to no longer fund or support the continuation of the study. The study team is unaware of any serious adverse events or

unanticipated risks to patients during the course of the study. Study participants will be offered a final close-out clinical examination visit of their study knee if they have not completed the study visits. This final research visit will be at no-charge to the patient or to their insurance company.

This final study visit will consist of a brief knee exam by a member of the study team and we will measure how well the patient can bend and straighten their knee (their range of motion). We would also ask the patient to answer a short survey about their knee function and pain. This survey is the same questionnaire the patient would have completed during the study at their regular study follow-up visits (the IKDC Knee Examination Form and IKDC Current Health Assessment Form). We anticipate this visit will take approximately 15-20 minutes. We still offer patient compensation of \$10 for completion of this final study visit.

If the patient is having any other issues with their study knee, with their knee on the other side, or any other orthopaedic problems and would like to see an orthopaedic surgeon, we will offer to schedule an appointment for the patient as a regular clinical visit. However, the patient and/or their insurance provider will be charged for this appointment.

If the patient chooses not to return to the clinic for the knee exam, we will ask them to complete the final brief survey about their knee function and pain. This survey may be completed either on the telephone or by email through an electronic survey. If the patient declines to participate in this final knee exam and/or survey, we will note their decision and not contact the patient any further about this study.

Patients will be transferred to clinical management of their knee and they will be followed as part of standard clinical care by their orthopaedic surgeon in the future.

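### Does the unreproducible 84.7% power figure, with its two unequal detectable differences and no stated time point, call for a change to the plan?

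*Combined protocol and SAP*

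**What the plan says.** The Sample Size section reports that one cited study "found a standard error of the mean (SEM) of 5.3 and a smallest detectable difference (SDD) of 14.6" for the IKDC subjective form. It then compares that study with a second: "These measures were slightly larger than the SEM of 4.6 and the SDD of 9.0". The conclusion drawn is: "Based on these values, power calculations identified the desired sample size as 50 patients in each surgical group to yield 84.7% power"; the full clause on power reads "to yield 84.7% power to detect a difference with an alpha = 0.05". No target difference, between-patient SD, test or sidedness is given there or elsewhere.

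On the endpoint, the Analytical Plan states: "The IKDC Subjective Knee Evaluation Form score will be the primary outcome measure". It names no time point. Under Patient assessments, "study participants will complete the subjective knee evaluation form at one month, three months, six months, and one year". The Objectives are narrower and directional: single-portal patients are expected to "have a higher International Knee Documentation Committee (IKDC) score at six months and one year".

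The closing Update to the study protocol records that the sponsor "has made a business decision to no longer fund or support the continuation of the study".

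**The concern.** Three things stand out.

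- **The two SDDs are not close.** The standard errors differ by 15%, but the SDDs differ by 62%. Required sample size varies with the inverse square of the difference, so the choice of target matters a great deal. A reader cannot tell which value, if either, was used.
- **The SDDs may rest on different formulas.** The abbreviation SEM is expanded as a standard error of the mean, but the printed numbers behave like standard errors of measurement. Neither quantity is the between-patient SD that a two-group power calculation needs.
- **The primary comparison has no stated side or time.** The score is collected at four post-operative times, and the hypothesis names two of them. If the time and side were chosen after seeing results, the nominal 5% would not hold.

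At stake would be the credibility of the trial's only power statement and control of its type I error.

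**Working it through.** **Inputs (Sample Size section).** SEM 5.3 and SDD 14.6 (first study); SEM 4.6 and SDD 9.0 (second study); 50 per group; alpha 0.05; power 84.7%. Not given: target difference, SD, test, sidedness, time point.

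**1. Trying to reproduce 84.7%.** Two-sample t-test, noncentrality = (difference/SD) × √(n/2), n = 50.

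- SDD as the difference, SEM as the SD: power above 99.9%.
- SEM × √50 as the SD, two-sided: about 22% to 28% for 9.0 points and 49% to 60% for 14.6.
- 9.0 as the difference with 14.6 as the SD: 86.3%. 5.3 with 9.0: 83.0%. These come near, but they use an SDD as an SD, which the text does not support.

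None gives 84.7%. Solving backwards, 84.7% needs a standardised difference of 0.603 two-sided or 0.537 one-sided. Two-sided, the implied SD is:

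- 9.0/0.603 = 14.9 if the target was 9.0;
- 14.6/0.603 = 24.2 if the target was 14.6.

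A single unstated SD could therefore yield the printed figure.

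**2. How far apart the two studies are.** SEM: 5.3/4.6 = 1.152. SDD: 14.6/9.0 = 1.622, and 1.622² = 2.63. At one common SD, two-sided, accepting 84.7% at 50 per group:

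| Target used | Implied SD | Power for the other SDD | n per group for the other SDD |
|---|---|---|---|
| 9.0 | 14.9 | 99.8% for 14.6 | 20 |
| 14.6 | 24.2 | 45% for 9.0 | 130 |

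The larger SDD needs fewer patients. The contrast also depends on holding the SD fixed. Suppose instead that each study's SD is proportional to its SEM (equal reliability, an assumption). The ratio becomes 2.63/1.152² = 1.98, the 45% becomes 56%, and the sample sizes become 26 against 50, or 50 against 99.

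**3. Basis of the SDDs.** 1.96 × √2 × 5.3 = 14.7, close to 14.6. The same formula with 4.6 gives 12.75, not 9.0, whereas 1.96 × 4.6 = 9.02. This suggests measurement error and two formulas, but it is inferred from numerical agreement alone; the cited papers would have to settle it.

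**4. Sidedness.** If 84.7% were one-sided, a two-sided test of the same 0.537 SD would have 75.8% power, and 63 per group would restore 84.7%. Nothing in the document says the test is one-sided.

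**5. Time points.** Two tests, each with 84.7% power, two-sided 5%, assumed between-time correlation 0 to 0.9:

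| Rule | Power | Type I error (no effect at either time) |
|---|---|---|
| Both six months and one year | 72% to 80% | 0.2% to 3.0% |
| Either suffices | not needed here | 7% to 10% |

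Zero correlation between repeated scores in the same patient is implausible, so the extreme ends are bounds. The Objectives join the two times with a conjunction; no passage states an either-time rule.

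**The case for a change.** The strongest argument for acting is that the time-point gap is real and cheap to close. One sentence in the Analytical Plan would name the primary time and the two-sided alpha, at no cost in patients or visits, and would remove the chance of choosing after the fact. Even in a stopped trial, whatever data exist may be compared. The power paragraph also cannot be audited as it stands.

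Much of this stands as description. The target difference, SD, test, side and primary time are unstated, and the wording that compares the two studies is fair for the SEM but not for the SDD. It falls short as a case for amendment, for three reasons.

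- No printed number or rule is shown to give a wrong answer. The power figure is undocumented, which is different from mistaken.
- The alarming consequences rest on readings the plan does not contain: a one-sided test, an either-time rule, or a search over all four visits.
- The remedy amounts to recording inputs that only the sponsor holds and making a choice of time that only the sponsor can make. A sentence naming a time would still leave the test, baseline adjustment and missing data to the analyst, so it would not by itself shut out post hoc choice.

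**Conclusion.** No change follows. The 84.7% cannot be reproduced from the text, but it is compatible with a detectable difference of about 0.60 SD (two-sided t-test, alpha 0.05, 50 per group, one time point). The gap between 14.6 and 9.0 is large, 62% and 2.63-fold in sample size at a common SD, but it matters only if one of them was the target. The understatement of that gap is a loose descriptor that feeds no stated calculation. The label and formula behind the SEM and SDD values are a query for the cited sources, not an established error.

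The missing side and time are gaps of the kind analysts fill sensibly. An unlabelled alpha of 0.05 is conventionally two-sided, and the Objectives point to six months and one year. Read as requiring both, that hypothesis costs power (72% to 80% for correlations of 0 to 0.9) but keeps type I error below 5% when there is no effect at either time.

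With support withdrawn and the number enrolled not given, power at 50 per group may not describe the data that will be analysed, and rewriting its justification would change no result. The conclusion would differ if the plan declared success at either time or at any visit; it does neither.
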